## 7.9 EXAMINATION SCHEDULE

Evaluation	
Study Visit #1/Adjustment #1	Day 0 (17 to 24 days post-implantation with the LAL)
Adjustment #2	3 to 7 days post Adjustment #1 Visit
Adjustment #3, if needed	3 to 7 days post Adjustment #2 Visit
Lock-in #1	3 to 7 days post final adjustment Visit
Lock-in #2, if needed	3 to 7 days post lock-in #1 Visit
Post Lock-In	7-14 days post final lock-in Visit
Postop Month 3	Days 75 to 120 post-implantation with the LAL

Unscheduled visits falling outside the designated ranges for scheduled visits will be considered “interim” visits for data recording purposes and a report form will be completed.

## 7.10 CLINICAL PARAMETERS

Clinical assessments when indicated will be performed in the following order:

1. Demographics
2. Ocular history including medications
3. Subjective symptoms/complaints (subject reported)
4. Compliance with UV spectacles
5. Autorefraction
6. Corneal Topography
7. Monocular UCDVA
8. Manifest Refraction
9. Monocular best corrected distance visual acuity (BCDVA)

[REDACTED]

12. Intraocular pressure
13. Slit Lamp Examination
14. Fundus Examination
15. Dilated pupil diameter
16. Spectral Domain OCT (if needed)
17. Adverse Event

Table 1. Schedule of Visits and Clinical Parameters

Visits	Study Visit #1/ Adjustment#1	Adjustment#2,	Adjustment#3, if needed	Lock-in#1	Lock-in#2, if needed	Postop Lock-in	Postop Month 3	Unscheduled Visit 
Demographics	X							
Ocular History	X							
History of Medications	X	X	X	X	X	X	X	X
Subjective Symptoms/Complaints (Subject reported)	X	X	X	X	X	X	X	X
Compliance with UV Spectacles	X	X	X	X	X			
Autorefraction	X	X	X	X	X	X	X	
Corneal Topography	X							
Monocular uncorrected distance visual acuity (UCDVA)	X	X	X	X	X	X	X	X
Manifest Refraction	X	X	X	X	X	X	X	
Monocular best corrected Visual Acuity Distance (BCDVA)	X	X	X	X	X	X	X	
[REDACTED]								
Intraocular Pressure	X	X	X	X	X	X	X	
Slit Lamp Exam	X	X	X	X	X	X	X	X
Fundus Exam	X						X	
Dilated Pupil Diameter	X	X	X	X	X			
SpectralDomain OCT	X 	X 	X 	X 	X 	X 	X 	X 
Adverse Events	X	X	X	X	X	X	X	X

Tests indicated with an “X” must be performed at each unscheduled visit. Other tests may be conducted based on the investigator’s assessment of the subject.

 If needed

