### **7.1.4 UV PROTECTIVE EYEWEAR**

- UV protective spectacles [REDACTED] are supplied to the patient as a two-pair set, with one having clear lenses for indoor use and the other pair with tinted lenses for outdoor use. Instruct the patient to wear the spectacles at all times indoors and outdoors, keeping the eyes closed when changing spectacles, until 24 hours post the final lock-in treatment.
- Alternatively, an optional patch can be used postoperatively. If used, the patient should be instructed not to remove the patch and keep it in place until the surgeon removes it at the one day post-operative visit. The UV protective eyewear will be provided once the patch is removed at the one day post-operative visit.
- For patients requiring spectacle correction for refractive errors in the fellow eye, “fitover” UV protective spectacles [REDACTED] are supplied to the patients as a two-pair

set, with one pair having clear lenses for indoor use and the other pair with tinted lenses for outdoor use. Instruct the patient to wear the “fitover” UV protective eyewear over their existing corrective spectacles at all times; keeping the eyes closed when changing spectacles.

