#### Lock-in light treatments

The study eye will receive a minimum of one lock-in treatment and a lock-in #2 may be performed, if necessary.

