## 7.6 PROCEDURE PREPARATION

Protocol-required measurements should be completed prior to adjustment or lock-in treatments.

The subject should be prepared for light treatments as follows:

Study eye undergoing a light treatment will be prepared for light treatment with pupil dilation.

1. The study eye will be dilated using pupil dilation drops  or pupil dilation gels  or pupil dilation agents of the investigator's choice. After waiting an appropriate amount of time for dilation to occur, the study eye will be examined to ensure that adequate dilation (enough of the edge of the LAL optic can be visualized to allow for centration during LDD light treatment) has been obtained. If adequate dilation has not been obtained, additional dilating drops with manual punctal occlusion or a sponge soaked in mydriatic medication and applied to the ocular surface can be utilized to try and gain further dilation. If adequate pupil dilation is still not achieved with the methods described above, the treatment will be rescheduled and the dilation attempted at another visit or another dilation method is used.
2. Once adequate pupil dilation is achieved, patch the subject's other eye and position the subject comfortably in front of the LDD with chin in the chinrest and forehead against the support bar. Ask the subject to grasp the handles on the LDD table for support. Inform the subject to concentrate on the green fixation light presented in front of them and to try and minimize eye movement.

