13. Upon completion of the lock-in #1 treatment, a notification may appear that informs the user that all required treatments are complete. If this notification appears, proceed to step #15. If no notification appears, then the subject will require a lock-in #2 treatment and proceed to step #14.
14. The subject will return for the second lock-in treatment 3 to 7 days after the first lock-in treatment.

---

15. The subject will be permitted to discontinue wear of the UV protective eyewear exactly 24 hours after the subject's final lock-in treatment for either eye (as appropriate) has been completed.

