#### **8.6.6 UV PROTECTIVE EYEWEAR COMPLIANCE**

Periods of non-compliance with UV protective eyewear will be reported based on the number of periods and time of non-compliance.

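### No scheduled question covers UV eyewear compliance after the final lock-in, so the Section 8.6.6 summary omits the last required wear period (24 hours for the study eye).

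*Combined protocol and SAP*

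**What the plan says.** - **Wear rule.** Section 7.1.4 has the patient wear the spectacles indoors and outdoors "until 24 hours post the final lock-in treatment". Step 15 of Section 7.8 allows the subject to stop "wear of the UV protective eyewear exactly 24 hours after" the final lock-in, and adds that the final lock-in of either eye counts, as appropriate.
- **Compliance question.** Section 7.10 lists "Compliance with UV spectacles" as an assessment. Table 1 in that section marks it at Study Visit #1/Adjustment #1, Adjustment #2, Adjustment #3, Lock-in #1 and Lock-in #2. The Postop Lock-in, Postop Month 3 and Unscheduled Visit cells are blank.
- **Order within a visit.** Section 7.6: "Protocol-required measurements should be completed prior to adjustment or lock-in treatments". The ordered list in Section 7.10 puts compliance fourth, ahead of dilated pupil diameter.
- **Number of lock-ins.** Section 7.3: "The study eye will receive a minimum of one lock-in treatment and a lock-in #2 may be performed, if necessary".
- **Next visit.** Section 7.9 sets the Post Lock-In visit (Postop Lock-in in Table 1) at "7-14 days post final lock-in Visit".
- **Reporting.** Section 8.6.6: "Periods of non-compliance with UV protective eyewear will be reported based on the number of periods and time of non-compliance". It states no cut-off at the final lock-in and names no other data source.

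**The concern.** The schedule stops asking about eyewear before the obligation to wear it ends. The question at a lock-in visit looks back over the interval since the previous visit. It cannot cover the hours after the treatment given later that day, and the next visit has no compliance item.

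What is at stake is the completeness of one safety summary. Section 8.6.6 reports how many periods of non-compliance occurred and how long they lasted. An interval nobody asks about can add neither periods nor time, so for that interval the error has one direction. The omission is also systematic: it comes from the schedule itself and not from occasional missing answers.

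**Working it through.** The plan gives no figure to reproduce here. The check sets the wear rule against the visit schedule and then sizes the uncovered interval.

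**Step 1. Is the table row read correctly?** The compliance row has five marks followed by three empty cells, as does the dilated pupil diameter row. Autorefraction has seven marks and one empty cell. The columns appear to be aligned and the row is not redacted.

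**Step 2. Coverage on each lock-in path.**
- Lock-in #1 is final: the last scheduled question comes before lock-in #1, and none comes after it.
- Lock-in #2 is final: the last scheduled question comes before lock-in #2, and none comes after it.

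The 24 hours after the final lock-in have a scheduled question on 0 of the 2 paths.

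**Step 3. Size of the interval for the study eye.** Inputs from Sections 1.3, 7.3 and 7.9: Adjustment #1 on day 17 to 24 after implantation, 3 to 7 days between treatments, two or three adjustments, one or two lock-ins.

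Final lock-in day = day of Adjustment #1 + gap × [(adjustments − 1) + lock-ins]. Required wear ends one day later.

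| Adjustments | Lock-ins | Final lock-in (day) | Wear ends (day) | One day as share of wear since implantation | One day as share of wear since Visit #1 |
|---|---|---|---|---|---|
| 2 | 1 | 23 to 38 | 24 to 39 | 4.2% to 2.6% | 14.3% to 6.7% |
| 2 | 2 | 26 to 45 | 27 to 46 | 3.7% to 2.2% | 10.0% to 4.5% |
| 3 | 1 | 26 to 45 | 27 to 46 | 3.7% to 2.2% | 10.0% to 4.5% |
| 3 | 2 | 29 to 52 | 30 to 53 | 3.3% to 1.9% | 7.7% to 3.4% |

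Extremes:
- Shortest path: 17 + 3 × 2 = 23, wear ends on day 24, 1/24 = 4.2%. Since Visit #1: 1/(24 − 17) = 1/7 = 14.3%.
- Longest path: 24 + 7 × 4 = 52, wear ends on day 53, 1/53 = 1.9%. Since Visit #1: 1/(53 − 24) = 1/29 = 3.4%.

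**Step 4. The fellow eye.** Step 15 of Section 7.8 counts either eye. If the fellow eye is locked in after the study eye, required wear runs beyond 24 hours after the study eye's last treatment, and the uncovered interval grows with it. The documents give no fellow-eye schedule, so this extension cannot be sized.

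**Step 5. Effect of one added question.** The Postop Lock-in visit falls 7 to 14 days after the final lock-in, which is 7 − 1 = 6 to 14 − 1 = 13 days after the study eye's wear requirement ends. A question there reduces the study eye's uncovered required time from 24 hours to zero. It leaves a remainder only where the fellow eye extends wear past that visit.

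**The case against.** **Other routes could pick up the non-compliance.** Section 11.7 requires any protocol deviation to be recorded on a case report form. Symptoms and adverse events are collected at the Postop Lock-in visit and at unscheduled visits, and Table 1 allows further tests at unscheduled visits. The case report forms, source templates and Appendix 1 are not in the documents reviewed. This stands in part: it would be wrong to say that non-wear in this interval can never come to light. But deviation reporting is passive, unscheduled tests are discretionary, and Section 8.6.6 refers to neither. They narrow the gap without closing it.

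**The interval is short and the outcome minor.** This stands. Section 8.6.6 is one descriptive line, Section 8.1.2 says there are no safety endpoints, and no effectiveness analysis uses compliance.

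**The row may be meant only as a check before treatment.** Its marks match those for dilated pupil diameter, which fits that reading, although the documents do not say so. If that is the intent, Section 8.6.6 should say that its reporting period ends at the final lock-in visit.

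A reader might also infer three stronger conclusions that the documents do not support:
- *That a subject who removes the eyewear on leaving the clinic would be reported as fully compliant.* Section 8.6.6 defines no such category, no compliance rate and no denominator.
- *That the gap hides an explanation for findings at the Postop Lock-in visit.* Section 9.12 ties its warning about unpredicted vision change from UV exposure to the time before the lens is locked in. Section 7.1.1 describes the shape change as permanent once the remaining photoreactive additive is consumed. The documents name no outcome for exposure in the last 24 hours.
- *That all 25 or more treated subjects are affected.* A subject who is explanted, dies or is lost before a final lock-in has no such interval.

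**Conclusion.** The point holds as a small, systematic gap in data collection. For every subject who reaches a final lock-in, the last required wear period has no scheduled compliance question, and for that period the Section 8.6.6 summary can only understate non-compliance.

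For the study eye the gap is 24 hours: 1.9% to 4.2% of required wear since implantation, or 3.4% to 14.3% since Visit #1. These shares assume that wear is counted from the day of implantation, that treatments fall within the scheduled windows with no postponement under Section 7.4, and that only the study eye determines the end of wear. The conclusion also assumes that the compliance question follows the Section 7.6 order and is asked before treatment.

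The change is worthwhile because it is cheap. The gap does not threaten the study's conclusions.

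**What to change.** In Table 1, mark the compliance item at the Postop Lock-in visit, worded to cover wear from the last visit to the end of the required period. Where a fellow-eye lock-in extended required wear past that visit, ask again at Postop Month 3. State in Section 8.6.6 that these periods are included in the count and the duration.

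The cost is one existing question at an existing visit, plus a conditional repeat. The downside is recall: 7 to 14 days back to the final lock-in at the Postop Lock-in visit, and longer at Month 3.

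If the sponsor prefers to leave Table 1 alone, the minimum is a sentence in Section 8.6.6 saying that reported compliance ends at the final lock-in visit. That makes the summary accurate about its coverage but leaves the interval unmeasured. Neither option alters the wear rule.

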## 7.11 DATA REPORTING

Electronic data capture (EDC) will be utilized for this study. Case report forms (CRFs) will be developed by the sponsor. In order to facilitate data entry, the CRFs coincide with the data entry pages in the EDC system. Research sites will be provided with source document templates (SDTs) that correlate with the CRFs. The appropriate SDTs will be completed and initialed or signed where indicated at each examination. All SDTs will be completed in a legible manner in black/blue ink.

Any corrections to the SDTs will be made by drawing a single line through the incorrect entry, recording the correct information, and initialing and dating the change. The study SDTs and data entered in the EDC system will be reviewed by the Study Monitor.

All clinical data generated in the study will be submitted to the RxSight Clinical Affairs Department or designated CRO for quality assurance review and statistical analysis. All SDTs and data entered into the EDC system will be reviewed for completeness and evident recording errors will be rectified by contact with the appropriate clinical site. Computerized data checks will be used to identify unusual data entries for verification prior to statistical analysis.

To minimize the amount of missing data, investigators will be trained on the deleterious effect that missing data have on trial integrity and credibility and that missing data could diminish the scientific value of all subjects' altruistic contributions.

## 7.12 STUDY COMPLETION PROCEDURES

An End of Study Form must be completed for all subjects enrolled in the study upon subject completion, withdrawal or discontinuation.

### 7.12.1 SUBJECT COMPLETION

Subjects are considered to have completed the study if the study eye has completed the Postop Month 3 examination.

Subjects with ocular serious adverse events or adverse device effects that are unresolved at study exit should continue to be followed until resolution of the event or until they are stable per the investigator's evaluation.

### 7.12.2 SUBJECT DISCONTINUATION AFTER LIGHT TREATMENTS

The subject will only be withdrawn from the study if the LAL is explanted in the study eye after Adjustment #1 or the subject has deceased.

The reason for discontinuation will be recorded on the appropriate study worksheet. Subjects who are discontinued from the study will still be a part of the study analyses up until the point they are exited. In the case of an explant, the investigator should continue follow-up for a period that ensures no adverse consequences have resulted. When possible, all necessary clinical assessments will be performed prior to the Subject exiting the study even if the assessment was not scheduled at that particular visit.

### **7.12.3 LOST TO FOLLOW-UP**

Subjects for which the final post-operative case report form is overdue and who refuse to be followed, or have difficulty being followed, or cannot be contacted despite extensive written and telephone follow-ups to determine the final clinical outcome, will be considered lost to follow-up. Sites must make a minimum of three documented attempts via telephone, email, or regular mail to contact the subject. If the subject does not reply to any of these attempts, the site must send a letter by certified mail (with a request for notification of receipt of delivery) to the subject. If a subject is non-responsive to these follow-up attempts, the subject will be considered to be lost to follow-up.

### **7.12.4 STUDY TERMINATION**

The study may be stopped at any time by the Sponsor for reasonable cause with appropriate notification. Conditions that may warrant study termination include, but are not limited to the following:

- Safety concerns. Clinical data from the study will be monitored to assure the safety of enrolled subjects.

If the clinical study is prematurely terminated, the Sponsor will inform the Investigator, the IRB, and other appropriate regulatory bodies. If the Sponsor terminates the study for safety reasons, it will immediately notify the Investigator, the IRB, and other appropriate regulatory bodies and provide an explanation of the reasons for termination. The Investigator will be provided with instructions for study termination and applicable subject follow-up. The Sponsor will continue to provide resources to fulfill the Clinical Study Plan obligations for follow-up of the subjects enrolled in the study.

## 8 STATISTICAL METHODS

### 8.1 SAMPLE SIZE CALCULATION

#### 8.1.1 SAMPLE SIZE FOR THE EFFECTIVENESS ENDPOINTS

There is no formal sample size calculation for this study. The comparisons for the effectiveness parameters will be made by descriptive statistics only. In order to have at least 20 LAL subjects (i.e. 20 LAL eyes) at 3 Months, a sample size of 25 subjects is needed with study eyes undergoing treatment based on spherical error combined with 0.50 D cylindrical refractive error.

[REDACTED]

The historical control groups will consist of all eyes that meet the requirements for inclusion in the respective group and each group will include a minimum of 25 eyes.

[REDACTED]

In refractive surgery, 20 eyes per one diopter bin is considered adequate for evaluation to demonstrate effectiveness of the refractive correction within that bin. As the LAL used in this study is an FDA approved, commercially available device, RxSight believes this approach to determining sample size is appropriate.

#### 8.1.2 SAMPLE SIZE FOR THE SAFETY ENDPOINTS

As the LAL that is used in this study is an FDA approved, commercially available device, there are no safety endpoints. Additionally, the LDD is also the FDA approved, commercially available device with the exception of the the availability of correction of 0.50 D cylinder.

#### 8.1.3 SAMPLE SIZE FOR THE STUDY

The planned study sample size of 25 enrolled subjects is sufficient.

### 8.2 GENERAL CONSIDERATION

The statistical analysis of the data will be performed using SAS version 9.3 or higher or another industry standard statistical software package. Continuous variables will be summarized using descriptive statistics, specifically the mean, median, standard deviation,

minimum and maximum. Categorical variables will be summarized by frequencies and percentages. The summaries will be provided for the LAL eyes that undergo 0.50 D cylinder correction (LAL treatment group) versus both the LAL historical control group and the Monofocal IOL historical control group. The 95% confidence interval for mean or for percentage may be provided.

### **8.3 BASELINE CHARACTERISTICS**

Demographics (such as age, gender, and race) and baseline characteristics will be summarized for the LAL treatment group, the LAL historical control group, and the Monofocal IOL historical control groups separately.

### **8.4 POPULATIONS FOR ANALYSIS**

#### **8.4.1 SAFETY POPULATION**

The safety population consists of any subject (or eye) who has signed the informed consent for participation in CSP-034 and has had the LDD light treatment attempted, which is defined as the point at which the light treatment is started. This population will be used for the safety analysis. No imputation will be performed.

#### **8.4.2 EFFECTIVENESS POPULATION**

The effectiveness population consists of study eyes of subjects who have signed the informed consent for participation in CSP-034, have had the LDD light treatments completed on the study eye, and who have completed a Postop Month 3 visit. This population will be used for the effectiveness analysis. No imputation will be performed.

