## 8.5 EFFECTIVENESS ANALYSES

Effectiveness analyses will be based on the Effectiveness population described in Section 8.4.2.

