### 8.5.2 ADDITIONAL EFFECTIVENESS ANALYSES

The following effectiveness outcomes will be summarized descriptively based on the observed data of the Effectiveness population, separately for the LAL treatment group, the LAL historical control group, and the Monofocal IOL historical control group. No imputation for missing values will be performed. The 95% confidence interval of the mean, if required, will be calculated based on the t-distribution; the 95% confidence interval of the proportion, if required, will be derived by the binomial distribution. It should also be noted that, for the MRCYL data analyses, the absolute MRCYL value will be used to present the summaries for simplicity.

 Baranyovits P. Stabilisation of refraction following cataract surgery. British Journal of Ophthalmology, 1988, 72, 815-819.

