### 8.5.2.1 Manifest Cylinder (MRCYL)

The MRCYL will be summarized beginning at Adjustment #1 using descriptive statistics for continuous outcomes stratified by the LAL treatment group, the LAL historical control group, and the Monofocal IOL historical control group. The number and percent of eyes with a MRCYL of  $\leq 0.25$  D, 0.50, 0.75 D, 1.0 D, and  $> 1.0$  D at each visit observed by either the LAL treatment group, the LAL historical control group, or the Monofocal IOL historical control group will be reported.

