#### **8.5.2.3 MRSE**

The measured MRSE, adjusted MRSE (to account for the measured distance of 4 meters) and change in MRSE from Adjustment #1 will be summarized by the descriptive statistics for continuous outcomes (such as mean and standard deviation) and the 95% confidence interval of the mean at each visit observed by subjects within the LAL treatment group, the LAL historical control group, and the Monofocal IOL historical control group respectively.

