## **8.6 SAFETY PARAMETERS**

The following safety outcomes will be summarized descriptively based on the observed data of the Safety population. The 95% confidence intervals for means or percentage may be presented, as appropriate.

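### LAL treatment group: every effectiveness table, including the by-visit ones, is limited to completers, which does not fit 7.12.2 and is not repaired by 8.6.2

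*Combined protocol and SAP*

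**What the plan says.** Section 8.4.2 restricts the effectiveness population to consented subjects who "have had the LDD light treatments completed on the study eye, and who have completed a Postop Month 3 visit", and rules out imputation. Section 8.5 states: "Effectiveness analyses will be based on the Effectiveness population described in Section 8.4.2". Section 8.5.2 adds that the further outcomes "will be summarized descriptively based on the observed data of the Effectiveness population".

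Several of those outcomes are reported by visit. Section 8.5.2.1 reads: "The MRCYL will be summarized beginning at Adjustment #1 using descriptive statistics for continuous outcomes". Section 8.5.2.3 reports MRSE "at each visit observed by subjects within the LAL treatment group". Absolute MRSE (8.5.2.5) follows the MRSE methods, and autorefraction (8.5.2.7) and UCDVA (8.5.2.8) are also given at each visit.

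On discontinuation, 7.12.2 says that a subject will "only be withdrawn from the study if the LAL is explanted in the study eye after Adjustment #1 or the subject has deceased", and then: "Subjects who are discontinued from the study will still be a part of the study analyses up until the point they are exited". Loss to follow-up is handled in 7.12.3, which is silent on analysis.

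The Safety population (8.4.1) holds every consented subject in whom a light treatment was started. Section 8.6.2 summarises MRCYL in that population at the *final scheduled visit*, a term that is not defined. On intervals, 8.6 says only: "The 95% confidence intervals for means or percentage may be presented, as appropriate".

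**The concern.** Membership of the effectiveness set depends on what happens after treatment starts. An eye can attend several visits, supply refractions and acuities at each, and then be removed from all effectiveness tables because it did not reach Month 3 or did not finish its light treatments.

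Some such exits could be related to the treatment: 9.12 foresees that adjustment or lock-in may worsen vision enough for the lens to be removed. Others, such as ordinary loss to follow-up, need not be related.

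The primary result is judged by numerical comparison and clinical assessment, with no test or margin (8.5.1). The reader therefore has to see how far the mean depends on which started eyes are left out. As written, no table is certain to show it.

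**Working it through.** **Step 1. Which started eyes appear where (treatment group).**

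| Started eye | Primary MRCYL (8.5.1) | By-visit effectiveness tables | 8.6.2 read as Month 3 | 8.6.2 read as last attended scheduled visit | Kept until exit by 7.12.2 |
|---|---|---|---|---|---|
| Treatments completed, Month 3 attended | in | in | in | in | not applicable |
| Treatments not completed, Month 3 attended | out | out | in | in | not addressed |
| Explant or death before Month 3 | out | out | out | in | yes |
| Month 3 missed or lost to follow-up | out | out | out | in | not addressed |

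The Month 3 reading is the natural one for treatment eyes: the schedule in 7.9 ends there, and 8.6.3 equates the final study visit with Month 3. On that reading 8.6.2 adds only the second row. On the other reading it adds all three excluded rows, but for MRCYL at one time point, with optional intervals and no change from baseline. For an eye that left before Adjustment #2, its only value would be the pre-treatment one. Neither reading supplies the by-visit tables or any MRSE, autorefraction or UCDVA summary. For the historical groups the term is more open, because their study ran 12 months (2.1) while the effectiveness comparison uses Month 6.

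**Step 2. How much observed data is set aside.** From the windows in 7.9, in days after implantation:

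- Earliest Post Lock-In: 17 + 3 + 3 + 7 = 30.
- Latest Post Lock-In: 24 + 7 + 7 + 7 + 7 + 14 = 66.
- Month 3 window: 75 to 120.

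Table 1 schedules manifest refraction and UCDVA at Adjustments #2 and #3, Lock-ins #1 and #2, and Post Lock-In. An eye that leaves before Month 3 can thus have 0 to 5 post-treatment refractions that no effectiveness table uses.

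**Step 3. The plan's own allowance.** Section 8.1.1 asks for 25 subjects to have at least 20 at Month 3. The implied loss is 20%, and 20/(1 − 0.20) = 25, so the figure reproduces. At that floor, 25 − 20 = 5 started eyes, or 5/25 = 20%, can be missing from every effectiveness table.

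**Step 4. Possible size (illustration only).** The documents give no exclusion rate, mean or SD. Assume a completer mean m = 0.25 D and a mean r for k excluded eyes of 25. If all eyes were counted, the mean would shift by k(r − m)/25. The 95% half-width for n = 25 − k completers is t × SD/√n, with SD assumed to be 0.15 to 0.35 D and t = 2.069, 2.074 and 2.093 for n = 24, 23 and 20.

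| k | r = 0.00 | r = 0.25 | r = 0.50 | r = 1.00 | Half-width |
|---|---|---|---|---|---|
| 1 | −0.01 | 0 | +0.01 | +0.03 | 0.063 to 0.148 |
| 2 | −0.02 | 0 | +0.02 | +0.06 | 0.065 to 0.151 |
| 5 | −0.05 | 0 | +0.05 | +0.15 | 0.070 to 0.164 |

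One or two eyes stay inside the half-width here. This is not guaranteed: with m = 0.10 D, two eyes at 1.00 D give 2 × 0.90/25 = 0.072 D, just above 0.065 D. Because every treatment eye enters at 0.50 D, mean change is mean MRCYL minus 0.50 D, so the same shifts apply to it.

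For the share at or below 0.25 D (8.5.2.1), if all completers qualify, the share of all started eyes lies between (25 − k)/25 and 100%: from 96%, 92% or 80% for k = 1, 2 or 5.

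**The case against.** The strongest defence is that a fixed completer cohort keeps the same eyes in the by-visit and primary tables, which is a reasonable choice in a descriptive study. Nor are explants hidden: secondary IOL intervention is among the events reviewed in 9.1, explants need expedited reporting (9.7), and an end-of-study form and a discontinuation reason are required (7.12, 7.12.2). Both points stand. They support keeping the completer analysis as primary, but they do not put the collected refractions into any effectiveness table.

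A reader might infer more than the documents support:

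- **A flat contradiction with 7.12.2.** That section speaks of the study analyses in general, and the safety tables honour it (adverse events, BCDVA by visit). It names only explant and death. The inconsistency is confined to effectiveness; including eyes lost to follow-up is a separate recommendation.
- **A flattering bias.** Excluded eyes could be worse than, better than or the same as completers. Nothing in the documents fixes the direction.
- **The same restriction in all three groups.** Section 8.4.2 requires consent to this study and a Month 3 visit, so it describes the treatment group. The historical group definitions (8.4.3, 8.4.4) are not in the visible text and cannot be checked.
- **The undefined visit in 8.6.2 as the cause.** The gap remains under either reading, so the wording is a secondary point.
- **A need to impute 0.50 D (no change) for missing eyes.** The plan excludes imputation, and that value could record an eye made worse as merely unchanged.

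**Conclusion.** The point holds for the LAL treatment group. Started eyes that were explanted, incompletely treated or missed Month 3 are absent from both primary MRCYL summaries and from the by-visit effectiveness tables for visits they attended. This does not fit 7.12.2 for discontinued subjects, and 8.6.2 does not make up for it.

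The size is limited and uncertain. Five of 25 eyes (20%) is the most that the allowance permits, not a forecast. On the assumed values, one or two eyes would probably shift the mean by less than its half-width. Five eyes at 1.00 D would shift it by 0.15 D, which exceeds the half-width for an SD of 0.15 D (0.070 D) but not for 0.35 D (0.164 D). These figures rest on assumed means and SDs. No stated figure in the plan is wrong. The change is worth making because it is cheap and uses data already collected.

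**What to change.** - Keep the 8.4.2 completer analysis as primary.
- Base the by-visit effectiveness tables on all started eyes (8.4.1) with observed data at that visit, and show n at each visit.
- Beside the primary result, report observed Month 3 MRCYL and change in MRCYL, with 95% CI, for all started eyes that have a Month 3 refraction.
- List each started eye outside the completer set with the reason, its last observed MRCYL, and the visit and treatment stage. Keep these values out of any mean. Only Post Lock-In follows the final treatment, it can fall as early as day 30, before the 2-month stability point cited in 8.5.1, and the visible text specifies two examiners only at the adjustment visits and Month 3.
- State in 7.12.2 that retention until exit covers the effectiveness tables, and name the visit meant in 8.6.2 for each group.

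The cost is SAP wording, one extra table set and one listing, with no new visits or measurements. The number of eyes will vary by visit. The added rows will be treatment-group only unless the same rule can be applied to the historical groups, and the tables should say so. Eyes with no Month 3 refraction will appear in the listing and not in the Month 3 mean, so some uncertainty remains but is visible.
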